# **Methods and Materials**

## 1.1. Study design and setting

This study was a double-blind case-control trial. In this study, the investigator was blind to the participant's measurements, the examiner and the observer were blind to the participant group. The study was conducted at the Security Forces Hospital in Dammam (SFHD), King Fahd Hospital of the University (KFUH) and Dammam Medical Complex (DMC) in Dammam, Saudi Arabia. This study was approved by the Institutional Review Board (IRB) at Imam Abdulrahman bin Faisal University (Appendix A).

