### **1.2.** Participants

The sample size was calculated using G\*power software Version 3.0.10. Data from Tambekar et al. (2016) was used (effect size 0.82,  $\alpha = 0.05$ , power= 0.95). The calculation resulted in a total of 51 participants. Lumbosacral radiculopathy patients with dominant peripheral sensitization of unilateral leg pain were recruited. The patient was diagnosed with peripheral sensitization if they fulfilled the criteria suggested by Schäfer et al. (2009) which included: S-LANSS score < 12, negative sensory and motor examination, and positive neural tissue provocation tests (straight leg raising test, slump test). The inclusion criteria were: adult, pain duration of more than 3 months, patients were diagnosed with peripheral sensitization. Patients with one or more of following criteria were excluded from this study: S-LANSS score  $\geq 12$ , motor or sensory deficits, history of back or lower extremity surgeries, bilateral referred pain, patients with TENS contraindications as described in Jones and Johnson (2009) such as pacemakers and cardiovascular problems, epilepsy, active malignancy, dermatological conditions, and diminished pain sensation.

At SFH, KFHU and DMC outpatients' clinics, the physician referred patients diagnosed with lumbar radiculopathy or lumbosacral radiculopathy with negative dermatomes, myotomes and reflexes examinations finding to the primary investigator. In the initial appointment, the primary investigator explained to each participant the aims and the general procedures of the study. If agreed to participate, the patient signed the consent form (Appendix B, C). The independent examiner started the examination for eligibility with S-LANSS assessment (Appendix D) and an examination of SLR and slump tests. If eligible, the patient was assigned alternatively to one of the three study groups: tensioner group (T- group), slider group (S- group), or control group (C- group). Patients were blinded to the intervention details until they were assigned to one of the study groups. In the alteration type of allocation of groups allocation, the first patient was assigned to slider group, the second was assigned to the tensioner and the third to control group. This order continued even if there was any withdraw until we reached the end of the list then we started filling the gaps in the list from the top with new participants.

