#### **1.3. Outcome measurements**

Evaluation procedures were carried out exactly the same for all the three group by an independent examiner. Another observer helped the examiner in recording hip and knee ROM during the examination. Both the examiner and observer were blinded to the study groups. The following measurements undertaken were carried out on four different occasions: baseline, after 1st session, after 3rd session, and after 6th session.

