### 1.3.1. Pain intensity

Visual analog scale (VAS) was used to measure pain intensity. It consisted of a 10-cm horizontal line with 'No pain" at one end and "Worst imaginable pain" at the other end. The patient was asked to mark his current leg pain level on the line. The Minimal clinically important difference (MCID) for VAS was reported to be 1.8 - 1.9 cm (Hägg et al., 2003). VAS is a valid and reliable measurement of pain intensity (Ferreira-Valente et al., 2011).

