### 1.3.2. Hip ROM with SLR

The patient was in supine position with their head in neutral and flat on the bed without pillows. The examiner supported the knee in full extension using his proximal hand, whereas distal hand was used to maintain the ankle position in a neutral position. The examiner passively raised the examined leg until the patient reported reproduction of his symptoms, or until the examiner felt significant resistance to SLR (Martin et al., 2014; Walsh and Hall, 2009a).

The independent examiner performed the SLR test for asymptomatic then symptomatic limb. A bubble inclinometer (Fabrication Enterprise Inc., White Plains, New York 10602, and U.S.A) was secured just proximal to the ankle joint using double adhesive tape. The inclinometer was directed towards the medial aspect of the leg so that the examiner could not see it. The observer adjusted the fluid to zero level before testing. The observer recorded the ROM when the patient started feeling reproduction of his symptoms or the examiner felt significant resistance (Figure 1).

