## 3.3.3 Knee flexion ROM with the Slump test

In the slump test, the patient seated at the edge of the bed with legs dangling freely and knee at an angle of 90° flexion. The patient's trunk was placed in slumped position with cervical flexion and hands were together behind the back. The distal hand of the examiner was used to maintain the ankle in neutral position. The examiner proximal hand was used to maintain the slump position of the patient trunk. The examiner instructs the patient verbally to maintain his head in flexed position. The examiner used his distal hand to passively extend the examined knee until the patient felt his symptoms, or until the examiner felt significant resistance (Walsh and Hall, 2009a). The measurement of knee flexion ROM in a slump was taken for the asymptomatic then symptomatic limb.

A bubble inclinometer was secured just proximal to the ankle joint using double adhesive tape. The inclinometer was directed towards the medial aspect of the leg so that the examiner could not see it. The observer adjusted the fluid to zero level before testing and recorded the angle during the test. The observer recorded the measurement of the inclinometer at the point of symptoms reproduction or the feeling of resistance (Walsh and Hall, 2009b) (Figure 2).

*Figure 1: Straight leg raising test. showing the placement of inclinometer to measure hip range of motion from starting position (A) to end position (B).* 

Figure 2: End position of the slump test. during which the observer was recording knee range of motion and the examiner performed the test.

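### The double-blind case-control label does not fit: the design described is an assessor-blinded, three-arm trial, so mobilisation-versus-TENS-only differences are open to patient expectation

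*Combined protocol and SAP*

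**What the plan says.** Section 1.1 opens with the design label: "This study was a double-blind case-control trial". The next sentence says who was blind to what: "the investigator was blind to the participant's measurements, the examiner and the observer were blind to the participant group". Section 1.3 repeats the assessor part: "Both the examiner and observer were blinded to the study groups". Patients appear in neither list.

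Section 1.2 says when patient blinding stopped: "Patients were blinded to the intervention details until they were assigned to one of the study groups". The same section allocates eligible patients in rotation to slider, tensioner and control.

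Under section 1.4 every arm receives TENS. The tensioner and slider groups also perform an active movement in a slump sitting position, in the same number of sets and repetitions. No sham movement is described for controls.

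There are three outcomes, measured at baseline and after sessions 1, 3 and 6:

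- VAS for leg pain (1.3.1): "The patient was asked to mark his current leg pain level on the line".
- Hip range in straight leg raising (1.3.2): the leg is raised "until the patient reported reproduction of his symptoms, or until the examiner felt significant resistance to SLR".
- Knee range in the slump test (3.3.3): the examiner's task is to "passively extend the examined knee until the patient felt his symptoms", with resistance felt by the examiner again as the alternative end point.

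In both range-of-motion tests the inclinometer faces away from the examiner and the observer takes the reading.

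**The concern.** Readers commonly take double-blind to include the patient, and a headline label is what gets carried into abstracts and risk-of-bias assessments. Here patients are not described as blinded after assignment, and the arms feel different: some patients do an exercise on top of TENS and others do not. A patient who expects the exercise to help may mark a lower VAS or report symptoms later in a provocation test. A blinded examiner cannot prevent that.

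What is at stake is how a difference between a mobilisation arm and TENS alone should be read. It would combine any effect of the technique with any effect of expectation, and the label suggests that the second part was controlled. The other half of the label, case-control, also misdescribes a prospective intervention study with allocated arms. It is a separate terminology error and adds nothing to the expectation argument, but the same edit removes it.

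**Working it through.** **1. Label against description.**

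| Party | Blinding described | Where |
|---|---|---|
| Examiner, observer | Blind to group | 1.1, 1.3 |
| Investigator | Blind to measurements; group not mentioned | 1.1 |
| Patient | Intervention details withheld until assignment; nothing after that | 1.2 |
| Whoever delivered treatment | Not identified | 1.4 and subsections |

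Only the assessors are blind to group during the treatment period. That is assessor blinding.

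**2. Exposure by outcome.**

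- VAS: the patient alone sets the value, so exposure is full.
- Straight leg raise and slump: the test ends at the patient's symptoms or at resistance felt by a group-blind examiner who cannot see the angle. Exposure is partial. The documents do not say how often each end point applies.

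**3. Exposure by contrast.** Slider and tensioner patients both do an active slump-position technique with the same sets and repetitions, plus TENS, so their expectations should be closer. Either arm against control compares an added exercise with none.

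**4. Security of the assessor blinding.** There are three assessments after baseline. No step is described to stop patients revealing their group to the examiner.

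**5. Illustrative size.** The plan has no figure of its own to reproduce.

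Inputs:
- Total of 51 (1.2). Assuming three equal arms, 51/3 = 17 per arm.
- Significance level 0.05 with Bonferroni post-hoc tests (1.5). Assuming three pairwise comparisons, 0.05/3 = 0.0167 each.
- Bias b between two arms, in SD units of the outcome compared: assumed 0.1, 0.25 and 0.5. True effect zero.

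For a two-sided, two-sample t-test:

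- degrees of freedom = 2 × 17 − 2 = 32
- non-centrality δ = b × √(17/2) = b × 2.915
- P(significant) = P(T > c) + P(T < −c), where T is non-central t with 32 degrees of freedom and non-centrality δ; c = 2.037 at 0.05 and 2.526 at 0.05/3

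| Assumed bias b | δ | At 0.05/3 | At unadjusted 0.05 |
|---|---|---|---|
| 0 | 0 | 1.7% | 5.0% |
| 0.1 SD | 0.292 | 2.1% | 5.9% |
| 0.25 SD | 0.729 | 4.6% | 10.9% |
| 0.5 SD | 1.458 | 15.9% | 29.3% |

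Against the nominal 1.7%, the adjusted rates are about 1.3, 2.8 and 9.5 times too high. The Bonferroni correction lowers the rates but does not remove the inflation, because the bias shifts the mean difference itself.

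**The case against.** The strongest reply is that the document is open about its blinding. Section 1.1 says who was blind immediately after the label, and 1.2 says that patient blinding ended at assignment. Nowhere does it claim protection from patient expectation. This stands. A reader might infer that the plan conceals the lack of patient blinding or asserts that expectation bias was excluded, and the text supports neither. But disclosing the details does not make the label accurate.

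A reader might also infer that the blinding is worthless or that all three outcomes are equally exposed. That is not supported either. Blinding the examiner and observer and turning the inclinometer away guard against assessor expectation, and both range-of-motion tests can end on the examiner's judgement. Only the VAS depends wholly on the patient.

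A third point is that patients know what they themselves do, but the documents do not say what they were told about the other arms, and TENS is a real treatment that can be felt. This stands as a limit on how large the bias might be. The consent material is not available to review, so nothing can be said about whether the patient information was neutral. Nor do the documents say who delivered treatment, so nothing can be said about that person's blinding.

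Finally, the bias sizes are assumed, and a pairwise t-test is simpler than the planned mixed ANOVA. At 0.1 SD the inflation is slight. The figures illustrate the mechanism and do not estimate the bias in this trial.

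**Conclusion.** The concern holds as a mislabelled design with a consequence for interpretation. The study is assessor-blinded, three-arm and parallel-group with alternate allocation. Protection from patient expectation is not delivered for mobilisation versus TENS-only. The gap is greatest for VAS, partial for the two range-of-motion outcomes, and smaller for slider versus tensioner. The assessor blinding is real, but no described step protects it from disclosure by patients.

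The size is unknown. For assumed biases of 0.1 to 0.5 SD, the false-positive rate per comparison runs from barely above nominal to roughly nine times nominal under the Bonferroni level. This rests on 17 per arm, three pairwise comparisons and no true effect. The conclusion about the label rests only on the text and does not depend on these figures.

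**What to change.** - **Section 1.1:** replace the design label with: *assessor-blinded, three-arm parallel-group trial with alternate allocation; patients were not blinded to group after assignment*. Keep the existing list of who was blind to what.
- **Section 1.5:** state that differences between either mobilisation arm and TENS alone, chiefly in VAS, include any patient-expectation effect, and that slider versus tensioner is the contrast least affected by it.
- **Section 1.3:** for any assessments still to be done, instruct patients before each one not to disclose their group to the examiner or observer. The text is in the past tense; if data collection is complete, this step no longer applies and the absence of such an instruction belongs with the limitations.

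The cost is a few sentences, with no extra patients or staff and no change to the planned tests. The downside is that the stated design becomes less favourable and the mobilisation-versus-TENS-only result must be worded more cautiously.

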### **1.2.** Participants

The sample size was calculated using G\*power software Version 3.0.10. Data from Tambekar et al. (2016) was used (effect size 0.82,  $\alpha = 0.05$ , power= 0.95). The calculation resulted in a total of 51 participants. Lumbosacral radiculopathy patients with dominant peripheral sensitization of unilateral leg pain were recruited. The patient was diagnosed with peripheral sensitization if they fulfilled the criteria suggested by Schäfer et al. (2009) which included: S-LANSS score < 12, negative sensory and motor examination, and positive neural tissue provocation tests (straight leg raising test, slump test). The inclusion criteria were: adult, pain duration of more than 3 months, patients were diagnosed with peripheral sensitization. Patients with one or more of following criteria were excluded from this study: S-LANSS score  $\geq 12$ , motor or sensory deficits, history of back or lower extremity surgeries, bilateral referred pain, patients with TENS contraindications as described in Jones and Johnson (2009) such as pacemakers and cardiovascular problems, epilepsy, active malignancy, dermatological conditions, and diminished pain sensation.

At SFH, KFHU and DMC outpatients' clinics, the physician referred patients diagnosed with lumbar radiculopathy or lumbosacral radiculopathy with negative dermatomes, myotomes and reflexes examinations finding to the primary investigator. In the initial appointment, the primary investigator explained to each participant the aims and the general procedures of the study. If agreed to participate, the patient signed the consent form (Appendix B, C). The independent examiner started the examination for eligibility with S-LANSS assessment (Appendix D) and an examination of SLR and slump tests. If eligible, the patient was assigned alternatively to one of the three study groups: tensioner group (T- group), slider group (S- group), or control group (C- group). Patients were blinded to the intervention details until they were assigned to one of the study groups. In the alteration type of allocation of groups allocation, the first patient was assigned to slider group, the second was assigned to the tensioner and the third to control group. This order continued even if there was any withdraw until we reached the end of the list then we started filling the gaps in the list from the top with new participants.

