### **1.5. Statistical analysis**

SPSS software (version 23, IBM Corporation, New York) was used for statistical analysis. Descriptive data of mean and standard deviation was obtained for all data. The baseline between groups' comparisons on clinical and demographic variables (BMI, age, and VAS) was performed using one-way analysis of variance (ANOVA). A two-way mixed design ANOVA (MANOVA) with post-hoc (Bonferonni Correction) was used to calculate the differences in outcomes measurements with TIME (baseline, 1st, 3rd, and 6th session) as a within-groups factor and GROUP (control, slider, and tensioner) as a between-group factor. The effect size was also calculated with Cohen's *d* to estimate the magnitude of differences within and between groups [small (d = 0.2), medium (d = 0.5), and large (d = 0.8)]. Pearson's correlation was performed to assess the relationship between pains, hip flexion ROM in SLR, knee flexion ROM in slump. The significant level was set at P < 0. 05.

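### Patients are allocated by a fixed slider–tensioner–control rotation with no random sequence or concealment described, so selection bias cannot be excluded and no planned between-group test is protected from it

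*Combined protocol and SAP*

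**What the plan says.** Section 1.2 describes alternation among three groups once eligibility is confirmed: "the first patient was assigned to slider group, the second was assigned to the tensioner and the third to control group". The order carries on despite withdrawals to the end of the list, and "then we started filling the gaps in the list from the top with new participants". A vacated place already belongs to a group, so the refills are as foreseeable as the main sequence. No section mentions a random sequence, envelopes, central assignment or an independent list holder.

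Before consent, "the primary investigator explained to each participant the aims and the general procedures of the study". An independent examiner then checks eligibility, and assignment follows.

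The stated blinding concerns other things. Section 1.1 says that "the investigator was blind to the participant's measurements, the examiner and the observer were blind to the participant group". Section 1.2 adds: "Patients were blinded to the intervention details until they were assigned to one of the study groups". Neither section says who knew the order.

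Section 1.1 gives the design as follows: "This study was a double-blind case-control trial". For the analysis, section 1.5 says: "A two-way mixed design ANOVA (MANOVA) with post-hoc (Bonferonni Correction) was used to calculate the differences in outcomes measurements with TIME" as the within factor and GROUP as the between factor. Cohen's d is planned "to estimate the magnitude of differences within and between groups". Baseline comparisons are listed for BMI, age and VAS. No adjustment for baseline is planned.

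**The concern.** A rotation balances the number of patients per group. It balances prognosis only if nobody can act on the order. When the next group is foreseeable, encouragement to join and the timing of enrolment can depend on it, whether deliberately or not. The groups may then differ in baseline pain, baseline range of motion, motivation or expected recovery.

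Blinding the examiner and observer to group protects the measurements, not the composition of the groups. A baseline comparison on three variables cannot rule out differences in the variables that it omits. At stake is whether a difference between slider, tensioner and control can be attributed to the technique.

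**Working it through.** The plan gives no figure for this point, so there is none to reproduce. The check has three parts.

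**1. Foreseeability.** The share of next assignments that can be guessed correctly by someone who knows all earlier ones:
- Fixed rotation: 100%.
- Randomly varying permuted blocks of 6 and 9, over 51 allocations, guessing the least-used arm: about 54% (simulation).
- Simple randomisation: 1/3 = 33.3%.

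**2. What a selected difference would do to the planned tests.** This is an illustration, because the documents give no size for any shift.

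Inputs:
- n = 51/3 = 17 per group (total from section 1.2; equal split assumed).
- Four visits (section 1.3).
- α = 0.05 (section 1.5).
- Assumed: no true effect, one group shifted by d = 0.5 SD (the medium value in section 1.5), and equal between-visit correlation r = 0.5 or 0.7.

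Let s_t be the shift at visit t and s̄ its mean over the four visits. With one group of three shifted, the between-group sum of squares carries the factor (2/3)² + 2(1/3)² = 2/3. The noncentralities are:
- GROUP (df 2, 48): λ = 17 × (2/3) × s̄² / ((1+3r)/4)
- GROUP × TIME (df 6, 144): λ = 17 × (2/3) × Σ(s_t − s̄)² / (1−r)

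| Shift over the four visits | r | s̄ | Σ(s_t − s̄)² | GROUP λ → rejects | GROUP × TIME λ → rejects |
|---|---|---|---|---|---|
| Constant: 0.5 throughout | 0.5 | 0.5 | 0 | 4.53 → 44% | 0 → 5% |
| Constant | 0.7 | 0.5 | 0 | 3.66 → 36% | 0 → 5% |
| Fading: 0.5, then r × 0.5 | 0.5 | 0.3125 | 0.0469 | 1.77 → 19% | 1.06 → 9% |
| Fading | 0.7 | 0.3875 | 0.0169 | 2.20 → 23% | 0.64 → 7.5% |
| Prognostic: 0, then 0.5 | 0.5 | 0.375 | 0.1875 | 2.55 → 26% | 4.25 → 27% |
| Prognostic | 0.7 | 0.375 | 0.1875 | 2.06 → 22% | 7.08 → 45% |

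Each test is inflated in at least one plausible pattern. The interaction keeps its level only when the shift is constant.

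**3. Which pairwise comparison to use.** The level is 0.05/3 = 1.7% (three pairs), with 17 per group, for one follow-up visit under the fading pattern:
- Raw follow-up values: bias r × d = 0.25 or 0.35 SD; rejects 4.6% or 7.8%.
- Change from baseline: standardised bias (1−r)d/√(2(1−r)) = 0.25 or 0.19; rejects 4.6% or 3.4%.
- ANCOVA on the baseline value: bias r × d − r × d = 0; rejects 1.5–1.7% in simulation.

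ANCOVA is not a cure. Under a constant shift it leaves d − r × d = 0.25 or 0.15 SD, where change scores leave none. Under the prognostic pattern the baseline carries no information about the shift, so all 0.5 SD remains.

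**The case against.** The strongest reply is that assignment comes after consent and after an eligibility examination by an independent examiner who is blind to group. This has weight, because it limits selection at the eligibility step. It does so only if the examiner did not know the order, which is not stated. It also does not cover the recruitment conversation, which the primary investigator holds before consent.

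A second reply is that the plan never claims randomisation and describes the alternation openly. That is correct: this is a design weakness, not a contradiction.

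Three stronger readings are tempting, and the documents do not support them:
- *Bias occurred, or the investigator knew the order.* The documents do not say who knew it. The investigator is stated to be blind to measurements; that this was the investigator's only blinding is an inference.
- *The case-control label conceals the non-random allocation.* The label is wrong for patients prospectively assigned to interventions, but section 1.2 discloses the method.
- *Only raw group comparisons are exposed and GROUP × TIME is safe.* That follows only if the shift is already present at baseline and stays constant or fades. A selected difference in prognosis with equal baselines reaches the interaction in full.

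If enrolment is complete, as the past tense suggests it may be, the allocation cannot be repaired. That limits the remedy but not the need to disclose.

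**Conclusion.** The concern stands. Allocation is a foreseeable rotation with no concealment described, and the stated blinding does not cover the order. Selection bias in the between-group comparisons cannot be excluded, and its size cannot be derived from the documents.

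The rejection rates above show sensitivity under an assumed 0.5 SD shift, 17 per group and assumed correlations. They do not estimate what happened in this trial. They show that no planned between-group test is protected, and that the choice of analysis reduces the exposure for some patterns of selection and not for others.

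**What to change.** **Patients still to be allocated, if any.** Replace the rotation and the gap-filling in section 1.2 with a computer-generated 1:1:1 list in randomly varying permuted blocks (for example 6 and 9). An existing person outside recruitment and assessment should hold it and open each assignment only after consent, eligibility and baseline measurement. If both methods were used, report results by allocation method. Cost: an amendment and list keeping, with no extra patients or visits.

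**Patients already allocated.**
- Section 1.1: replace the case-control label with *quasi-randomised (alternation) controlled trial*, and state who held and knew the order.
- Section 1.1 or 1.2: state that between-group p-values do not rest on random, concealed allocation.
- Section 1.5: base between-group comparisons on follow-up values adjusted for the baseline value of the same outcome (ANCOVA, Bonferroni-corrected) instead of raw group differences. Report the planned GROUP × TIME test alongside. If this is chosen after results are known, say so.
- Section 1.5: state that no analysis removes bias from selection on unmeasured prognosis.

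Cost: wording changes and a reanalysis of data already collected.

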## **1.4. Interventions**

Each patient received therapeutic sessions over 2 weeks (3 sessions/ week). All patients in all groups received Transcutaneous Electric Nerve Stimulation (TENS). In addition, T-group received tensioner neural mobilization technique and S-group received slider neural mobilization technique.

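### Withdrawn patients are replaced in the same group and nothing says their data are analysed; the planned mixed ANOVA would then compare completers plus replacements, which is biased if response-related withdrawal differs between groups

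*Combined protocol and SAP*

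**What the plan says.** Section 1.2 allocates by a fixed rotation: "the first patient was assigned to slider group, the second was assigned to the tensioner and the third to control group". Withdrawals do not disturb it: "This order continued even if there was any withdraw until we reached the end of the list". After that, "then we started filling the gaps in the list from the top with new participants". Each position belongs to one group, so a replacement enters the group of the patient who left. The text does not say so outright, but the rotation implies it.

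On numbers, section 1.2 states "The calculation resulted in a total of 51 participants", which is 51/3 = 17 per group if the groups are equal. Section 1.3 says "The following measurements undertaken were carried out on four different occasions": baseline and after sessions 1, 3 and 6. Section 1.4 sets the treatment period: "Each patient received therapeutic sessions over 2 weeks (3 sessions/ week").

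Section 1.5 names the software ("SPSS software (version 23, IBM Corporation, New York) was used for statistical analysis") and a two-way mixed-design ANOVA, with time as the within-patient factor and group as the between-patient factor. No section defines an analysis set, follow-up after withdrawal, a missing-data rule, or a use for the measurements of a patient who withdrew. No number, timing or reason of withdrawal is given.

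**The concern.** Read together, sections 1.2 and 1.5 lead to a particular comparison. A patient who leaves after session 1 or 3 has no session-6 value, so the standard repeated-measures ANOVA drops that patient completely, including the measurements already taken. A new patient who finishes takes the position. The final table can then show 17 complete patients per group and give no sign of who left, when or why.

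This matters if patients leave because of how they are responding and do so differently between groups. Such a difference is plausible here: patients learn their intervention at assignment, and all groups receive TENS but only two add neural mobilization. A group that loses its poor responders looks better than it should. A harmless pattern and a harmful one would look the same to a reader of the results.

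**Working it through.** **No figure to reproduce.** The plan gives no withdrawal rate, outcome SD or bias estimate. All inputs below except 51 patients, three groups, four occasions and the 1.8 cm VAS difference are assumptions.

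**1. Formula.** Let p = withdrawn/allocated in a group and g = mean outcome of withdrawn patients minus mean of completers. Omitting withdrawn patients shifts that group's mean by p x g in absolute size. The bias in the comparison of groups A and B is p_A x g_A - p_B x g_B. Refilling does not appear in the formula: a replacement is another draw from the patients who complete.

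**2. Proportions.** With 17 completers and 2 or 4 withdrawn patients in one group:
- 2/(17+2) = 2/19 = 0.105
- 4/(17+4) = 4/21 = 0.190

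**3. Only one group loses patients, for response-related reasons.** Simulation with 1,000,000 patients per group: normal outcomes, correlation 0.6 between any two of the four occasions, withdrawal after session 3, logit slope 1.0 per SD of pain, intercept set to give p.

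| Withdrawal depends on | p | g (SD) | Completer bias p x g (SD) | Bias with all available data, likelihood-based (SD) |
|---|---|---|---|---|
| observed session-3 pain | 0.105 | 0.55 | 0.06 | below 0.001 |
| observed session-3 pain | 0.190 | 0.52 | 0.10 | below 0.001 |
| unobserved session-6 pain | 0.105 | 0.91 | 0.10 | 0.05 |
| unobserved session-6 pain | 0.190 | 0.87 | 0.17 | 0.09 |

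The completer bias is therefore 0.06-0.17 SD. A likelihood-based analysis removes it when withdrawal depends on recorded pain and about halves it when withdrawal depends on pain never recorded.

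**4. Same withdrawal rule in two groups, with a true effect.** Assumed SD 2 cm, withdrawal driven by session-3 pain, true difference 0.9 cm at session 3 and 1.80 cm at session 6. The group with less relief loses more patients:
- 10.5% v 7.2% withdrawn: completer difference 1.77 cm, bias 1.80 - 1.77 = 0.03 cm
- 19.2% v 13.7% withdrawn: completer difference 1.75 cm, bias 1.80 - 1.75 = 0.05 cm

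Both run towards no difference.

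**5. Cases with no bias.** With the same rule in both groups and no treatment effect, the completer difference is within 0.01 cm of zero. With unequal withdrawal unrelated to response (20%, 10% and 5%), a separate simulation of 20,000 trials with 17 completers per group gives bias 0.00 SD and type I error 0.05.

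**6. Scale.** The standard error of a difference between two groups of 17 is sqrt(2/17) = 0.343 SD. Step 3 is therefore 0.06/0.343 = 0.17 to 0.17/0.343 = 0.50 of a standard error. At SD 2 cm the standard error is 0.686 cm, so step 4 is 0.03/0.686 = 4% to 0.05/0.686 = 7% of it. Section 1.3.1 states: "The Minimal clinically important difference (MCID) for VAS was reported to be 1.8 - 1.9 cm". Against 1.8 cm, step 4 is 0.03/1.8 = 1.7% to 0.05/1.8 = 2.8%.

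**The case against.** The strongest reply is that replacing withdrawn patients is harmless and that the rest is argued from silence. Three parts of it stand.

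- A reader might infer that refilling itself biases the comparison. It does not: omitting withdrawn patients gives the same bias whether or not their places are filled. Equal group sizes are a reasonable aim, and refilling need not stop.
- A reader might infer that the investigators discarded withdrawn patients' data. The documents do not say so, and they do not say the data were kept. Exclusion follows from how the named analysis normally works.
- A reader might infer a large bias. Loss of 4 of 21 in one group only, a full 1.0 SD gap and an SD of 2.5 cm would give 0.190 x 1.0 x 2.5 = 0.48 cm, or 26% of 1.8 cm. Losing 30% from both mobilization groups and none from control, with only below-average responders leaving, would give 0.34 SD and a type I error of 0.17. No withdrawal figure in the documents supports either case, and a two-week course limits the time for withdrawal. Where a true effect alone drives the difference, the distortion is a few hundredths of a centimetre and would not create a false benefit.

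The reply does not remove the gap. Followed as written, the plan leads to a completer comparison, and nothing in it lets a reader separate the harmless cases from the others.

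**Conclusion.** The point holds as a conditional one and should be addressed. The analysed set is likely to be completers plus replacements. The comparison is then biased if response-related withdrawal differs between groups, either in rate or in reason. Neither size nor direction can be derived from the documents. Under the stated assumptions the bias ranges from zero, through 0.03-0.05 cm towards no difference, to about 0.06-0.17 SD, which is at most about half a standard error. If withdrawals took place before any session for unrelated reasons, there is no bias. Confidence is medium, because the analysis set and the timing of withdrawals are both unstated.

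**What to change.** 1. In sections 1.2 and 1.5, state that every allocated patient, including those who withdrew and were replaced, is analysed in the allocated group. Replacements may stay as additional patients, flagged as such.
2. In section 1.5, replace the mixed ANOVA with a linear mixed model for repeated measures on all available assessments (SPSS MIXED, REML, unstructured covariance). Say that it assumes data are missing at random and may not remove all bias.
3. Report number, timing and reasons of withdrawal by group, separating patients who left before any post-baseline measurement.
4. Give the completer analysis as a sensitivity check.
5. If a worse-outcome check is added, vary the shift by group and name the imputation method, since the mixed model itself produces no imputed values. A common shift of 1.8 cm moves the comparison by 1.8 x (p_A - p_B), which is zero when rates are equal. It would miss, for example, 15% withdrawal in every group with poor responders leaving the mobilization groups and good responders leaving control. In simulation that pattern gives a bias of 0.28 SD.

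The cost is small: another procedure in the same software, one table, a few sentences, and slightly unequal group sizes. The estimate may move in either direction. The text is in the past tense, so if withdrawn patients' measurements were not kept, only the withdrawal reporting and a correspondingly cautious conclusion remain possible.
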